## **1 Protocol Outline**

### **Title**

Early Treatment of Borderline Pulmonary Arterial Hypertension Associated with Systemic Sclerosis (SSc-APAH)

**Short title:** EDITA

**Local Project ID:** 2014-05ED

### **Phase**

IIA (proof of concept)

### **Financing/ Status of the Sponsor**

Co-financing by pharmaceutical industry GlaxoSmithKline GmbH

### **Indication**

Clinical phenotype systemic sclerosis-patients with borderline-PAH: mean pulmonary arterial pressure (mPAP) values at rest (between 21-24 mmHg) and/or elevated mPAP during exercise (>30 mmHg, with transpulmonary gradient (TPG) >11 mmHg and pulmonary artery wedge pressure (PAWP) < 15 mmHg at rest and <18 mmHg at exercise).

I27.0 Primary pulmonary hypertension

M34.9 Systemic sclerosis, unspecified, or

M35.8 Other specified systemic involvement of connective tissue

MedDRA (V. 12.0)

Systemic Sclerosis ID 10042953, Level 4

Pulmonary Hypertension 10037400, Level 4

EudraCT: 2014-001882-28	3.1 Version 29.04.2016 final	EDITA
-------------------------	------------------------------	--------------

## **Trial Population**

### Inclusion Criteria

Male or female SSc patients with borderline - PAH and

1. mPAP 21-24 mmHg, TPG > 11 mmHg, PAWP <15 mmHg and/or
2. Exercise induced elevated mPAP-values >30 mmHg, PAWP <18 mmHg; TPG >15 mmHg, as defined in Saggari et al. (2012) without left heart or severe lung disease or systemic arterial hypertension
3. Adult patients having completed his/her 18th birthday
4. Patients with definite diagnosis of Systemic Sclerosis using the scleroderma criteria of the American Rheumatism Association
5. SSc-disease duration >3 years
6. Able to understand and willing to sign the Informed Consent Form
7. Negative pregnancy test at the start of the trial and appropriate contraception throughout the study for women with child-bearing potential.

### Exclusion Criteria

1. Any connective tissue diseases (CTD) other than SSc
2. Pulmonary hypertension (PH) confirmed by right heart catheter (RHC) before enrolment, i.e. mPAP  $\geq$ 25 mmHg at rest
3. Patients presenting normal mPAP values, i.e. mPAP <21 mmHg at rest, and  $\leq$ 30 mmHg during exercise, and/or PAWP  $\geq$ 15 mmHg at rest or  $\geq$ 18 mmHg during exercise
4. Ongoing or a history of >2 weeks of continued use of therapies that are considered definitive PH treatment: endothelin receptor antagonists (ERA; e.g. bosentan, ambrisentan), phosphodiesterase type 5 inhibitors (PDE5; e.g. sildenafil, tadalafil, vardenafil), prostanoids (e.g. epoprostenol, treprostinil, iloprost, beraprost) and soluble guanylate cyclase stimulator (e.g. Riociguat). Intermittent use of PDE5 inhibitors for male erectile dysfunction is permitted.
5. Except for diuretics and corticosteroids medical treatment should not be expected to change 4 weeks prior inclusion into the study and during the entire 12-week study period.
6. Known intolerance to ambrisentan or one of its excipients
7. Clinically significant anemia (hemoglobin concentration of less than 75% of the lower limit of normal, LLN)
8. Forced vital capacity (FVC) <60%, forced expiratory volume in first second (FEV1)

EudraCT: 2014-001882-28	3.1 Version 29.04.2016 final	EDITA
-------------------------	------------------------------	--------------

<65%

9. Severe interstitial lung disease, idiopathic pulmonary fibrosis
10. Renal insufficiency (glomerular filtration rate [GFR] <60 mL/min/1.73m^2 at least for the last 3 months before inclusion)
11. Baseline values of hepatic aminotransferases (ALT and/or AST) >3 x upper limit of normal (ULN)
12. Systolic blood pressure <85 mmHg;
13. evidence of inadequately treated blood pressure >160/90 mmHg and/or blood pressure during exercise >220/120 mmHg
14. Patients referred with clinically significant overt heart failure
15. Clinically significant fluid retention
16. Previous evidence or diagnosis of clinically relevant left heart disease, i.e. at least one of the following: Previous echocardiography with estimated left ventricular (LV) ejection fraction <50%, previous history of cardiogenic pulmonary edema, increased size of left atrium (>50 mm)
17. Known significant diastolic dysfunction associated with clinical heart failure
18. Known coronary disease or significant valvular heart disease
19. Known congenital heart defects such as single ventricle, transposition, Eisenmenger
20. Known hypertrophic cardiomyopathy or left ventricular hypertrophy (interventricular septum thickness (IVS) or posterior wall thickness (PWD) >1.2 cm)
21. Participation in any clinical drug trial within 4 weeks prior to screening of this study and/or who is scheduled to receive another investigational medicinal product (IMP) during the course of this study
22. Pregnancy or lactation

## **Objectives**

### Primary [Objectives/ Endpoints]

1. Determine whether mPAP of SSc patients with borderline-PAH (mPAP 21-24 mmHg, TPG ≥11 mmHg) can be reduced by 3 mm Hg (absolute change baseline vs. 6 months; equals 15%) by treatment with ambrisentan 10 mg/die (may be initiated with 5 mg/die and escalated to 10 mg/die) over 6 months (primary endpoint) compared to baseline and placebo.

### Secondary Objectives

2. Determine whether exercise induced elevated mPAP-values (>30 mmHg without left

EudraCT: 2014-001882-28	3.1 Version 29.04.2016 final	EDITA
-------------------------	------------------------------	--------------

heart or severe lung disease or systemic arterial hypertension) and further measures of exercise capacity, symptoms and quality of life can be reduced by ambrisentan 10 mg/die over 6 months

3. Analyze if the progression (adverse events, hospitalization, initiation of pulmonary hypertension treatment) of borderline-PAH to manifest PH can be avoided by ambrisentan-treatment (descriptive, observational)
4. Assessment of tolerability and safety

### Secondary Endpoints

Analyze if in patients with SSc and borderline-PAP show an improvement by treatment with ambrisentan 10 mg/die over 6 months in:

- 6-Minute-walking test
- Quality of life (QoL, SF-36)
- Echocardiography: right atrial area (RA-area), right ventricular area (RV-area), Tei, Tricuspid Annular Plane Systolic Excursion (TAPSE), systolic pulmonary arterial pressure (sPAP)
- Lung function tests: forced expiratory flow (FEV1), total lung capacity (TLC), diffusion-limited carbon monoxide (DLCo), DLCo/alveolar volume (VA), forced vital capacity (FVC), forced expiratory volume in one second (FEV1), residual volume
- Borg Dyspnea Index
- WHO-functional class
- further invasively measured hemodynamic parameters evaluated by RHC: right atrial pressure, pulmonary vascular resistance, cardiac output (CO), cardiac index (CI), PAWP, venous oxygen saturation (SvO2)
- Raynaud-syndrome and skin involvement, assessed by the modified Rodnan-Skin score and Symptoms of Scleroderma (descriptive)

### **Trial Design**

Patients with borderline PAH indicated by borderline mPAP values will be included in this single centre study. This clinical investigation is performed as a Proof-of-Concept (PoC) investigator initiated trial (IIT) using a prospective, randomized, double-blind, parallel group, placebo-controlled, phase IIA clinical study design. On their first visit their medical history will be obtained and physical examination will be conducted. Moreover, an electrocardiogram (ECG), laboratory testing (NT-proBNP, uric acid and other laboratory tests), echocardiography

EudraCT: 2014-001882-28	3.1 Version 29.04.2016 final	EDITA
-------------------------	------------------------------	--------------

at rest and right heart catheterization will be carried out. If patients have been identified within the last 6 months before screening investigations by right heart catheterization, the measurements are considered valid as baseline investigations and will not be repeated. If patients fulfill the inclusion criteria and still suffer from borderline mPAP values they will be invited to join the study. The clinical investigations will begin within 28 days. The prospective study will comprise a 6 months study period ( $180 \pm 2$  weeks) plus the screening phase up to 28 days and a follow-up phase of  $30 \pm 7$  days.

### **Investigational Medicinal Product(s) (IMPs)**

#### **IMP: Test treatment**

Ambrisentan [Volibris®] once daily starting at 5 mg/die in the beginning of the study. Dosage will be up-titrated to 10 mg/die after 1-4 weeks according to the physician's and the patient's estimation.

Study medication will be provided orally with or without food. Treatment effect will be controlled at each study visit and the dose will be adapted. The patient will take one or two tablets of ambrisentan 5 mg once daily.

#### **IMP: Placebo**

Placebo tablets with the same treatment regimen (once daily) as the verum therapy will be provided. One pill a day will be given. Treatment effect will be controlled at each study visit and the sham dose will be adapted. The patient will take one or two tablets once daily.

### **Sample Size**

In this randomized, controlled, double-blind study patients with borderline PAH will be randomized into two groups: one group receiving ambrisentan and one Placebo. The main comparison will be the difference in treatment effect between ambrisentan arm and placebo. The primary endpoint will be the change of mean pulmonary arterial pressure between baseline and after 6 months compared to placebo.

Based on previous data and the inclusion criteria we expect a baseline mPAP of 20 mmHg, a mean reduction of 3 mmHg (equals 15%) with standard deviation of the difference of 2.5 mmHg. To reject the null hypothesis with 90 percent probability if the means of the mPAP differ by at least 3 mmHg (17 vs. 20 mmHg, 15%) a sample of 15 patients in each group is required, according to the two-tailed Student's t-test, with a type I error of 0.05 (two-sided) and equal standard deviations of 2.5 mmHg in both patient groups.

EudraCT: 2014-001882-28	3.1 Version 29.04.2016 final	EDITA
-------------------------	------------------------------	--------------

Due to the fact that the borderline-PAP-group is defined by an mPAP of 21-24 mmHg the sample will have a small standard-deviation. The effect of lowering the mPAP in SSc-APAH-patients by 15% has been reached in several studies as in Klinger et al. (2011). In order to cover a possible 20% drop-out rate, we will include 19 patients in each group = 38 patients in total.

The sample size was calculated by means of a two-sided two-sample t-test. Primary efficacy analysis will be performed by an analysis of covariance (ANCOVA) model including baseline scores as covariate, thereby yielding a power advantage over the standard t-test used for sample size calculation. The calculated sample size will thus provide 90% power or more.

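### The 90%-or-more power claim is marginally unsupported: the named t-test gives 88.7% at 15 per group, the ANCOVA gain is not quantified, and the entry window is no evidence for the SD of the change

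*Protocol*

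**What the plan says.** All the relevant text is in the protocol's Sample Size section; the SAP as supplied contains no power statement.

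- **Target and test.** The aim is "To reject the null hypothesis with 90 percent probability" for a 3 mmHg difference, with a two-tailed Student's t-test at a two-sided type I error of 0.05. On that basis "a sample of 15 patients in each group is required", raised to 19 per group (38 in total) for 20% drop-out.
- **SD.** The figure appears as a "standard deviation of the difference of 2.5 mmHg" and again as "equal standard deviations of 2.5 mmHg in both patient groups". The expected values are said to rest on previous data and on the inclusion criteria. A further sentence argues: "Due to the fact that the borderline-PAP-group is defined by an mPAP of 21-24 mmHg the sample will have a small standard-deviation".
- **ANCOVA.** The primary analysis adjusts for baseline. This is said to improve on the t-test used for sizing, and the section concludes: "The calculated sample size will thus provide 90% power or more". No baseline-to-change correlation, regression slope or baseline SD is given.

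**The concern.** The closing sentence presents 90% as a floor. It reasons that the t-test already delivers 90% and that ANCOVA can only add to it. Neither step is secured. The t-test named in the text falls slightly short of 90% at 15 per group. ANCOVA gains power only if baseline predicts the change; otherwise it costs one degree of freedom.

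The reason offered for a small SD concerns the wrong quantity. The endpoint is the change in mPAP over 6 months, whereas an entry window restricts the baseline reading.

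At stake is how a null result from a 38-patient proof-of-concept trial would be read. A reader should know that the power is about 89% under the stated assumptions if the full drop-out allowance is used, and that it depends on an SD of the change for which the window gives no support.

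**Working it through.** **Inputs (Protocol, Sample Size):** difference 3 mmHg; SD 2.5 mmHg in each group, taken as the SD of the change; alpha 0.05 two-sided; target power 90%; 15 evaluable and 19 randomized per group.

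**1. Reproducing the plan's figure.** Normal approximation:

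n = 2 × (1.960 + 1.282)² × 2.5² / 3² = 14.6, rounded up to 15 per group.

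The same approximation gives 90.8% power at 15. Drop-out: 15 / 0.80 = 18.75, rounded up to 19. So 15 and 19 are both reproduced, but by the normal formula.

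**2. The test the protocol names.** Two-sample t-test, noncentral t with 2n − 2 degrees of freedom and noncentrality 3 / (2.5 × √(2/n)). At n = 15 the noncentrality is 3.29 on 28 degrees of freedom, with critical value 2.05.

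| Evaluable per group | t-test power |
|---|---|
| 15 | 88.7% |
| 16 | 90.7% |
| 17 | 92.4% |
| 18 | 93.8% |
| 19 | 94.9% |

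The shortfall at 15 is 90 − 88.7 = 1.3 points, or one patient per group.

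**3. ANCOVA at 15 per group.** Let r be the correlation of the change with baseline. The residual SD is 2.5 × √(1 − r²), with 2n − 3 = 27 degrees of freedom. Chance baseline imbalance multiplies the variance of the estimated effect by about 1 + 1/(2n − 4) = 1 + 1/26. The documents give no r, so the values below are assumed.

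| Absolute r | Ignoring imbalance | Allowing for imbalance |
|---|---|---|
| 0 | 88.6% | 87.5% |
| 0.1 | 88.9% | 87.8% |
| 0.2 | 89.8% | 88.7% |
| 0.3 | 91.3% | 90.3% |
| 0.4 | 93.3% | 92.4% |

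Power reaches 90% at r² of about 0.045 (r about 0.21) ignoring imbalance, or about 0.08 (r about 0.28) allowing for it.

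**4. The entry window.** The variance of the change is b² × Var(baseline) + residual variance, where b is the slope of change on baseline. Restricting baseline reduces the first term only. Measurement error and biological variation at 6 months are in the second term, which the window does not touch.

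Nor does the window apply to every patient. The inclusion criteria join the resting range and the exercise criterion by and/or. Exclusion criterion 3 turns away a resting mPAP below 21 mmHg only when the exercise value is also not raised. The Sample Size section itself expects a mean baseline of 20 mmHg, below the window.

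**5. Sensitivity to the SD of the change (assumed values either side of 2.5; the documents give no range).**

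| SD of change | 15 per group | 19 per group |
|---|---|---|
| 2.0 mmHg | 97.7% | 99.4% |
| 2.5 mmHg | 88.7% | 94.9% |
| 3.0 mmHg | 75.3% | 85.1% |

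**The case against.** **The arithmetic gap is trivial.** It is 1.3 points, the normal formula returns exactly 15, and the trial randomizes 19 per group. One fewer loss per group than allowed takes the t-test past 90% without any ANCOVA gain. All of this stands, and it is why the point is minor. It does not rescue the wording, because the protocol attaches 90% to 15 per group and then calls it a minimum.

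**The closing sentence is about ANCOVA, and a modest correlation suffices.** This also stands. A reader might infer that the claimed power is false or that the trial is underpowered. The documents do not support that: with no correlation given, the claim is undemonstrated rather than refuted.

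**The SD also rests on previous data.** The section says so, and those data cannot be assessed from the documents. The criticism therefore reaches only the window sentence and does not show that 2.5 mmHg is wrong. Power at a larger SD is a sensitivity figure, not evidence of an error; an SD of 2.0 would give about 98%.

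**Stronger claims about the window.** A reader might infer that the window removes most of the ANCOVA gain, or that 2.5 mmHg is impossible because values confined to 21-24 have an SD of at most 1.5. Both require every resting value to lie in the window, which the and/or criteria and the expected mean of 20 mmHg contradict. Even inside the window, assuming a baseline SD of 0.87 to 1.15 mmHg and slopes from −0.25 to −1, ANCOVA power at 15 per group (allowing for imbalance) runs from about 88% to 94%. It is also too absolute to say that the window leaves the SD of the change untouched, since it removes some of the baseline-explained part.

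**The two uses of 2.5 mmHg.** They can be read together as an SD of the change that is equal in both groups. The comparison of 17 with 20 mmHg is worded as levels rather than changes. That calls for clarification; it does not prove a contradiction.

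**Conclusion.** The point holds as a minor one. On the plan's own inputs, the two-sided t-test has 88.7% power at 15 evaluable patients per group, and 16 are needed for 90%. ANCOVA at 15 per group has about 87.5 to 88.6% power if baseline is unrelated to the change. It passes 90% once baseline explains about 4.5 to 8% of the variance of the change. That may well happen, but the plan gives nothing to show it, so 90% is not a guaranteed minimum.

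The entry window is not evidence for the SD of a 6-month change, and it does not bind patients who enter by the exercise criterion alone.

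These figures assume that 2.5 mmHg is the SD of the change in each group and that the true difference is 3 mmHg. They do not show that the trial is too small: with all 19 per group evaluable, t-test power is about 95%.

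**What to change.** Reword the protocol's Sample Size section as follows:

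1. State the power as: *With 15 evaluable patients per group and an SD of the change of 2.5 mmHg in each group, the two-sided t-test has about 89% power (about 95% if all 19 per group are evaluable).*
2. Delete the words *or more*, or make the higher figure conditional on a stated baseline-to-change correlation.
3. Say explicitly that 2.5 mmHg is the SD of the change.
4. Remove the sentence that derives a small SD from the 21-24 mmHg window.
5. Optionally, add a symmetric sensitivity line labelled as an assumption: at 15 per group, about 98% power at SD 2.0 mmHg and about 75% at SD 3.0 mmHg.

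No patients are added and the analysis is unchanged. The only cost is that the stated power becomes slightly less favourable.

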## **Statistical Analysis**

### General

#### Descriptive statistics:

All data (demographic and other baseline characteristics, continuous data at each visit and their change to baseline) will be listed and trial summary tables will be provided.

Descriptive statistics will be displayed by treatment and placebo corrected for the active treatment group (arithmetic mean, median, standard deviation, standard error, 95% confidence limits of mean and median, first and third quartiles, minimum, and maximum for quantitative variables). Frequency tables for qualitative data will be provided.

#### Primary efficacy parameter:

The main parameter is the mPAP after 6 months compared to baseline. The differences will be compared between treatment and placebo group along with baseline mPAP as covariate using a covariance analysis.

#### Secondary efficacy parameters:

Secondary efficacy analysis comprises hemodynamics, vital signs, electrocardiogram, echocardiography, systemic sclerosis characteristics, laboratory parameters, pulmonary function, 6-minute walking distance, quality of life questionnaire, safety parameters adverse events and concomitant medication.

EudraCT: 2014-001882-28	3.1 Version 29.04.2016 final	EDITA
-------------------------	------------------------------	-------

## 1.1 Flow Chart/ Trial Schedule

	Randomized; double-blind controlled study including 38 patients with “borderline-PAH”				
Assessment	Screening “borderline-PAH” day -28/-1 Visit 1*	Baseline o day 1* Visit 2	After 3 months/ 90 days ± 2weeks Visit 3	After 6 months/ 180 days ± 2weeks Visit 4*	30±7 days Follow-up by phone
Written Informed Consent, obtained before any study procedure	X				
Check of eligibility criteria	X	X			
Demographics (height)	X				
Medical History	X				
Randomization		X			
Physical Examination	X	X	X	X	
SSc characteristics		X		X	
Modified Rodnan Skin Score and Symptoms of Scleroderma		X		X	
Vital Signs (blood pressure, heart rate, oxygen saturation, body weight)	X	X	X	X	
WHO functional class	X	X	X	X	
Electrocardiogram		X	X	X	
Pulmonary function tests: DLCo, DLCo/VA, FVC, FEV1, TLC, residual volume; blood gas analysis		X		X	
Local lab assessment #	X	X	X	X	
Pregnancy test (serum or urine)	X	X	X	X	
Echocardiography	X	X		X	
Right heart catheterization** (RHC), at rest, during exercise	X			X	
Quality of life Questionnaire SF-36		X		X	
6MWD, Borg Dyspnea Index		X	X	X	
Adverse events (AE)		X	X	X	X
Concomitant medication	X	X	X	X	
Concomitant disease	X	X	X	X	X
Study medication and Diary hand out or check		X	X	X	

o In borderline-PH-patients the screening assessment of PH screening (screening study, accepted by the Ethics committee University of Heidelberg) may be used as baseline examination for the randomized, double-blind part of the study when the screening assessment is not older than 28 days.

\* according to hospital practice possible in-hospital stay

\*\* Baseline-RHC may be up to 6 months old at inclusion, continuous ECG, CO and SvO2 recording during haemodynamic investigations

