4.1 Definitions

All patients randomized and treated will be valid for the intention-to-treat analysis population. A randomized patient is valid for the intention-to-treat, if at least one dose of study medication was administered. A patient is valid for per-protocol analysis, if the patient has an adequate hemodynamic measurement at baseline and after 12 weeks or if withdrawn due to lack of efficacy, who has an adequate hemodynamic assessment at any time post-baseline up to 12 weeks, and shows no major protocol deviation.

Major protocol deviations are:

1. Patients who do not meet the inclusion criteria
2. Administration of study medication not according to protocol (e.g. compliance less than 80% or greater 120%)

The above specifications of the analysis populations are in accordance with the recommendations given in the ICH-E9 Guideline “Note for guidance on statistical principles for clinical trials”.

The safety set comprises all patients who have been included in the study.

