4.2 Application

Efficacy analyses will be performed for the intention-to-treat analysis set. A sensitivity analysis for the primary endpoint will be performed with the per-protocol set.

Safety analyses will be performed with the safety set.

5 Trial centres

Zentrum für pulmonale Hypertonie, Thoraxklinik am Universitätsklinikum Heidelberg

6 Analysis variables

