7.1 Missing values

Variables with more than 20% missing values will be excluded. For all others, a complete case data analysis for each variable will be performed. No imputation method will be applied.

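### The primary analysis labelled intention-to-treat covers only patients with a Visit 4 catheterisation, and nothing in the supplied text requires that catheterisation for patients who stop study drug early

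*Protocol*

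**What the plan says.** **Schedule.** In Protocol 1.1 (Flow Chart/ Trial Schedule), the row "Right heart catheterization (RHC), at rest, during exercise" is marked at Visit 1 (screening) and Visit 4 (180 days ± 2 weeks). Visit 3 has no catheterisation. There is no early-termination column, and the only later contact is a telephone call. SF-36, lung function and skin score are measured at baseline and Visit 4. Echocardiography is also done at screening, but its only post-baseline measurement is at Visit 4.

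**Analysis set.** SAP 4.1 places every randomised patient with at least one dose in the intention-to-treat set. SAP 4.2 states: "Efficacy analyses will be performed for the intention-to-treat analysis set". Its only sensitivity analysis of the primary endpoint uses the per-protocol set.

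**Missing data.** For variables that are kept, SAP 7.1 says that "a complete case data analysis for each variable will be performed", with no imputation.

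**Sample size.** The protocol says "a sample of 15 patients in each group is required" and raises this to 19 per arm: "In order to cover a possible 20% drop-out rate".

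**Withdrawn patients.** The per-protocol definition in SAP 4.1 also admits a patient "if withdrawn due to lack of efficacy, who has an adequate hemodynamic assessment at any time post-baseline", up to 12 weeks.

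**The concern.** The primary variable is the change in mPAP from baseline to 6 months (SAP 8.5), and one catheterisation supplies its post-baseline value. A dosed patient without that catheterisation belongs to the intention-to-treat set by definition but is absent from the primary ANCOVA. The per-protocol analysis recovers none of these patients, since it only removes more.

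Reasons for stopping may differ by arm: side effects on ambrisentan, lack of effect on placebo. If they do, patients with a 6-month value are no longer comparable between arms in the way randomisation made them, and the estimate may not apply to the population that the label names. Any later repair rests on assumptions that the trial cannot test. Several secondary endpoints share the gap, because they too have a single post-baseline measurement at Visit 4.

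**Working it through.** **1. The plan's own figure.** The inputs are in Protocol, Sample Size: "To reject the null hypothesis with 90 percent probability if the means of the mPAP differ by at least 3 mmHg", "with a type I error of 0.05 (two-sided) and equal standard deviations of 2.5 mmHg in both patient groups".

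- Normal approximation: n = 2 × (1.960 + 1.282)² × 2.5² / 3² = 14.6, so 15 per arm (power 90.8%).
- Exact t-test: power at 15 per arm is 88.7%; 16 per arm are needed for 90%.
- Drop-out: 15 / 0.8 = 18.75, so 19 per arm and 38 in total.

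The sample size reproduces to within one patient per arm and is not in dispute. It does show that the plan treats drop-outs as lost to the primary analysis: 19 − 15 = 4 per arm, or 8 of 38.

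**2. How the loss could move the estimate.** Assume a mean change of −3 mmHg in 15 ambrisentan completers and 0 in 15 placebo completers, with 4 patients missing per arm. The completers' difference is 3.0 mmHg. The difference over all 19 per arm would be:

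| Assumption about the missing patients | Ambrisentan mean | Placebo mean | Difference (mmHg) |
|---|---|---|---|
| Like completers in both arms | −3.00 | 0 | 3.00 |
| Ambrisentan: no change; placebo: like completers | (15 × −3 + 4 × 0)/19 = −2.37 | 0 | 2.37 |
| Ambrisentan: like completers; placebo: +3 | −3.00 | (15 × 0 + 4 × 3)/19 = +0.63 | 3.63 |
| Ambrisentan: no change; placebo: +3 | −2.37 | +0.63 | 3.00 |

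These scenarios are not bounds. If the ambrisentan drop-outs rose by 3 mmHg while the placebo drop-outs resembled completers, the difference would be (45 − 12)/19 = 1.74 mmHg.

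**3. The per-protocol clause against the schedule.** SAP 4.1 relies on a haemodynamic assessment within 12 weeks in patients withdrawn for lack of efficacy. The nearest visit is Visit 3 (90 days ± 2 weeks), which has no catheterisation. A value by 12 weeks could not supply the 6-month endpoint in any case.

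**4. Power if stoppers are measured at day 180.** Assume that all 38 have Visit 4, that 20% stop drug, and that stoppers on ambrisentan keep a share of the 3 mmHg effect. Exact t-test, 19 per arm, SD 2.5:

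- all of the effect kept: 3.0 mmHg, power 94.9%;
- half kept: 0.8 × 3 + 0.2 × 1.5 = 2.7 mmHg, power 90.0%;
- none kept: 0.8 × 3 = 2.4 mmHg, power 82.1%.

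In the last case, mixing stoppers with completers raises the ambrisentan variance to 2.5² + 0.2 × 0.8 × 3² = 7.69. Averaged with 6.25 for placebo, the SD is √6.97 = 2.64 and power is 77.8%. Restoring 90% would take 24 per arm (SD 2.5) to 27 per arm (SD 2.64).

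**5. A linked point in SAP 7.1.** The same section drops any variable with more than 20% missing and makes no exception for mPAP. The planned loss of 8 of 38 is 21.1%. Read literally, the rule would then remove the primary variable.

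**The case against.** A reader might infer that a patient who stops drug can never contribute an mPAP. The documents do not say so. Visit 4 is fixed at day 180 and is not restricted to patients on treatment. No supplied passage says that stopping drug ends participation. Compliance below 80% removes a patient from the per-protocol set only, and SAP 8.5 does not exclude off-drug values. The protocol text available is an outline with a flow chart, and SAP 2 and SAP 9 refer to withdrawal criteria that it does not show. The haemodynamic clause in SAP 4.1 may reflect a withdrawal procedure set out elsewhere. This objection stands: the gap is one of silence, not prohibition.

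A reader might also take 20% as the expected rate of early stopping. The protocol calls it possible and uses it as a sample-size allowance. It also covers patients who withdraw consent or are lost, whom no visit rule can recover.

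Nor do the documents support a fixed overstatement. The 2.37 mmHg scenario implies 3/2.37 = 1.27, or 27%, but only if drop-outs differ from completers in one arm alone; with both mechanisms together, the difference returns to 3.00 mmHg.

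It would also be too strong to say that no analysis could help. Sensitivity analyses can show how far missing values could move the result, and Visit 3 data on walking distance, Borg index and functional class could inform them.

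Finally, a proof-of-concept trial may prefer an on-treatment question. That is a legitimate choice, but it does not match the intention-to-treat label that the SAP uses.

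**Conclusion.** The point holds as a gap between label, schedule and analysis rule. In the supplied text, the only post-baseline catheterisation is at Visit 4, nothing requires it after early stopping, and SAP 7.1 confines the primary analysis to patients who have it. The one clause that mentions haemodynamics in withdrawn patients relies on an assessment that no visit provides, on a time scale that conflicts with the 6-month endpoint.

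The direction of any bias is unknown. Under the four tabulated scenarios, with 4 missing per arm, the all-patient difference lies between 2.4 and 3.6 mmHg around 3.0, and there is no bias if drop-outs resemble completers. Those inputs are assumptions, since the documents give no data on drop-outs. If the full protocol already requires Visit 4 after stopping, the data-collection part falls away. The analysis rule, the missing-data sensitivity analysis and the 12-week wording would still need attention. This is worth correcting, but it is not evidence that the planned result is biased by any given amount.

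**What to change.** - **Flow chart.** State that patients who stop study drug but still consent remain in follow-up and have the Visit 4 assessments, including the catheterisation already planned for them, at day 180 ± 2 weeks. This does not touch when or why drug is stopped.
- **SAP 8.5.** State that day-180 values count in the intention-to-treat primary analysis whether or not drug was stopped. Use any catheterisation done earlier, at stopping, only in a sensitivity analysis.
- **Sensitivity analysis.** Add a delta-adjusted or tipping-point analysis for patients still without a 6-month mPAP.
- **SAP 4.1.** Reconcile the 12-week wording with the 6-month endpoint and with the visits that exist.
- **SAP 7.1.** While editing, exempt the primary variable from the 20% exclusion rule.

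The text changes are small, and each patient's Visit 4 catheterisation is already planned. The real costs are that some patients will decline a further invasive test after stopping, and that off-drug values may dilute the effect. If 20% stop and lose all effect, power at 19 per arm is about 78–82%, against 88.7% for 15 completers per arm at the full 3 mmHg. If stoppers keep half the effect, it is about 90%.
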